1.0 Research Design

1.1 Purpose/Specific Aims

The purpose of this study is to find an alternative, low risk option for managing muscle soreness in the older adult and elderly population.

A. Objectives

This study aims to compare how the topical application of essential oils *Eucalyptus globulus* and *Mentha x piperita* impact delayed onset muscle soreness after eccentric exercises compared to one another and to control.

B. Hypotheses / Research Question(s)

It is hypothesized that application of *Eucalyptus globulus* or *Mentha x piperita* oil will reduce perceived muscle soreness in subjects compared to control.

1.2 Research Significance

Delayed onset muscle soreness (DOMS) is a common resultant of activity which exceeds one's typical range. Its effects linger, often beginning 8 to 24 hours after activity and peaking within 24 to 48 hours of repetitive eccentric exercises. [1] Elite athletes must frequently cope with this during the peak of their training, but the average person also experiences its effects following the initiation of an activity regimen or an increase in their routine. It is thought that this phenomenon is multifactorial in nature, with proposed mechanisms including lactic acid retention, damage to connective tissue, and local inflammation. [2] Swelling due to influx of fluid and immune cells into muscle tissue is also a contributing factor. [1] There are a multitude of proposed management strategies for DOMS, ranging from pharmacological approaches like NSAIDs and analgesics, exercise, stretching, cryotherapy, transcutaneous electrical nerve stimulation, ultrasound, fish oils, caffeine, and antioxidants, among others. [1] These methods have varying efficacy and consistency in improving the effects of DOMS, and furthermore they each have their potential for adverse effects or lack of accessibility.

Herbal and natural medicine has been around for many years, particularly in regard to inflammatory disorders and somatic symptoms. As more research into the efficacy of these alternative methods is performed, they become an even more viable option. Essential oils, through aromatherapy, topicals, or ingestion, have been employed for a wide variety of ailments including those of anti-bacterial, anti-oxidant, and anti-inflammatory nature. [3] These oils are generally regarded as safe to use as well, as is proclaimed by the U.S. Food and Drug Administration, particularly when used at appropriate diluted concentrations topically when the risks are minimized further. [4] These oils might be a potential alternative or additive to usual management of muscle soreness, particularly in patient populations like the elderly who are more susceptible to the side effects of medications like NSAIDs.

Oils under the genus *Eucalyptus* and *Mentha* have been shown to have anti-inflammatory and analgesic properties. [5,6,7] Both have been shown to have inhibitory effects on nitrous oxide and reduce the activity of various inflammatory markers. [5,8] *Eucalyptus globulus* is predominantly comprised of 1,8-cineole, which can inhibit neutrophil migration and thereby reduce edema and inflammation. [9] Rodent studies have even shown that *Eucalyptus* may have antinociceptive effects similar to that of morphine [8], which is supported by the subjective pain relief it brought to patients following a total knee replacement. [10] *Mentha x piperita* has been studied for its topical analgesic effects in headache patients, and application appeared to help suppress temporal muscle activity. [11] Local application has been shown to have a cooling effect through alteration of the calcium channels for cool-receptors, which may be soothing. [12] With these benefits in mind, this study aims to identify and compare the effects of topical *Eucalyptus globulus* and *Mentha x piperita* oils in delayed onset muscle soreness in the older adult and elderly population.

1.3 Research Design and Methods

This study is designed as a randomized controlled interventional study with a rolling enrollment over the course of 6 months, with each individual subject's participation spanning over 72 hours. 20 subjects will be recruited for participation. 10 subjects will be included in the *Eucalyptus globulus* intervention group, and the remaining 10 will be placed in the *Mentha x piperita* group. A blocked randomisation list will be generated using an online randomizer in order to allocate subjects to each treatment group randomly. Each subject will have one upper extremity serving as the control, and one upper extremity which receives the intervention.

A. Research Procedures

Subjects

Subjects 50 years old and above with no previous resistance training sessions within the past year will be recruited at The Manor Health and Rehabilitation, a subacute rehabilitation and long-term care facility. A verbal explanation will be provided to the potential subjects by [name] or [name] on-site at the facility, including the fact that their care at the facility will not be affected by their decision to participate or not, and if they are interested in proceeding they will be asked to complete a survey regarding the subject's demographics (gender, age, hand dominance), ensure there are no hypersensitivities to the oils being used, upper extremity injuries within 1 year, and that they have the functional capacity for exercise of 3.5 metabolic equivalents or greater based on the Duke Activity Status Index. Subjects will be required to sign a consent to participate in screening. If participants pass the screening process they will again be informed of the study and all potential risks/benefits prior to signing an informed consent to partake in research.

Materials

Eucalyptus globulus and Mentha x piperita essential oils will be obtained commercially from SunRose Aromatics (Morrill, Maine), and, individually, will be mixed with carrier oil for application. SunRose Aromatics is a recommended supplier from the RJ Buckle Clinical Aromatherapy for Health Professionals course. Fractionated coconut oil will be used as the carrier oil and also obtained from SunRose Aromatics. A 2% oil mixture for topical application will be made with essential oils diluted in fractionated coconut oil per guidelines from the RJ Buckle Clinical Aromatherapy for Health Professionals course recommendations. This mixture will be prepared directly before application of oils by [name] or [name]. The unmixed oils will be stored in a private room with no windows at room temperature at the Manor Health and Rehabilitation facility ([name]).

Intervention

Participants will be divided equally into the *Mentha x piperita* or the *Eucalyptus globulus* group. A 2% oil mixture for topical application will be made with essential oils from SunRise Aromatics diluted in fractionated coconut oil per guidelines from the RJ Buckle Clinical Aromatherapy for Health Professionals course recommendations. Physiciansupervised eccentric exercise of the elbow flexors will be performed based on an adaptation of the method described by Weber. [14] Free weight dumbbells will provide resistance. The subject will be instructed to prolong the extension aspect of the curl to be five seconds long. They will repeat this motion for 10 or more repetitions until exhaustion, either due to the participant feeling they can no longer tolerate the five second eccentric aspect of the exercise or the investigator identifying that their form has faltered. If subjects reach exhaustion after the 10 repetitions minimum, they will rest for 1 minute. If they are unable to complete 10 repetitions at this weight, the resistance will be decreased to the next lowest weight and they will continue until exhaustion. This will continue until subjects reach exhaustion with the lowest resistance weight. Immediately following exercise, the participants will have the respective oil applied topically to their left upper extremity by the investigator. Their right upper extremity will serve as the control and no essential oil will be applied. Investigators will apply the oil without any use of massage technique and to only apply very superficial pressure. This application will be repeated 8 hours after exercise, when DOMS has been known to initiate, and at 24 hours after exercise, when DOMS may begin to peak.

Subject Safety

Vital signs will be measured prior to the initiation of exercise, including temperature, heart rate, blood pressure, and oxygen saturation. A physician will be notified of any abnormalities and the subject must be medically optimized prior to exercising. All exercise will be supervised by a physician. After the intervention is applied, subjects will be directly observed for 15 minutes by a physician to ensure no immediate adverse reactions occur. Vital signs will be repeated at the end of the observation period.

Nursing staff will be on-site in their usual capacity and physicians available on-call throughout the duration of the study. Medications are available at the facility if needed for any adverse events.

B. Data Points

Subject outcomes will be based on a self-reported visual analog scale, which has previously been shown to have validity in subjectively quantifying perceived muscle soreness and used in prior studies. [14,16]. These outcomes will be recorded by investigators for both the intervention and control upper extremity at 24, 48, and 72 hours post-exercise.

C. Study Duration

Each subject will participate in this study for 72 hours. The overall study is anticipated to take place over a six month duration.

D. Endpoints

The primary endpoint will be a self-reported perceived muscle soreness using a visual analog scale. There are no secondary endpoints.

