4.0 Subject Considerations

4.1 Subject Selection and Enrollment Considerations

A. Method to Identify Potential Subjects

Research staff will identify patients who are currently admitted at the facility for subacute rehabilitation or long-term care that meet the age criteria of 50 years or older

B. Recruitment Details

Potential subjects will be verbally informed of the opportunity to participate in the study by co-investigators [name] and [name] at the Manor Health and Rehabilitation center, and if interested full details allowing for informed consent would be provided by the investigators. Subjects will be informed that their decision to participate or not participate in the study would have no influence on their care at the facility.

C. Subject Screening

The co-investigators will administer a simple screening survey to interested subjects which identifies basic demographics, such as age, gender, and hand dominance, history of upper extremity injuries within the past 1 year, open proximal upper extremity wounds, any allergies/hypersensitivities to the oils involved. The patient's functional status for exercise based on the Duke Activity Status Index will also be assessed, and they must have a score equivalent to 3.5 or greater metabolic equivalents (METs). Potential subjects will sign a screening consent prior to partaking in this screening survey.

Inclusion Criteria

Subjects 50 years or older with no previous resistance training sessions in the past year and who are currently admitted at the Manor Health and Rehabilitation facility will be recruited.

Exclusion Criteria

Exclusion criteria included any history of musculoskeletal injury or weight bearing restrictions to the upper extremities within the past year. Participants cannot have any significant symptoms that would preclude them from exercising without medical clearance based on the American College of Sports Medicine's "Recommendations for Preparticipation Health Screening," [13] and those with an asymptomatic history of any cardiovascular, metabolic, or renal disease must have a functional capacity of at least >3.5 METs based on the Duke Activity Status Index to participate in the type of exercises that are part of this study, based on the American College of Sports Medicine's "2011 Compendium of Physical Activities." [20] Subjects with known adverse

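### Eccentric work per arm is not fixed, not stated to be matched and not listed for recording, so a left-right work difference in either direction could not be told from an oil effect

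*Combined protocol and SAP*

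**What the plan says.** **Amount of exercise.** Section 1.3 (Intervention) sets a floor but no total: "They will repeat this motion for 10 or more repetitions until exhaustion". There are two ways to reach exhaustion. The first is the participant's own limit: "either due to the participant feeling they can no longer tolerate the five second eccentric aspect of the exercise". The second is "the investigator identifying that their form has faltered". A subject who cannot reach the minimum steps down: "the resistance will be decreased to the next lowest weight and they will continue until exhaustion". This goes on to exhaustion at the lightest weight. Neither a starting weight nor a number of steps is given, and nothing says whether the two arms work together or in turn.

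**Allocation.** "A blocked randomisation list will be generated using an online randomizer in order to allocate subjects to each treatment group randomly". This concerns the type of oil only. The side is fixed: "the participants will have the respective oil applied topically to their left upper extremity by the investigator", and "Their right upper extremity will serve as the control and no essential oil will be applied". Section 1.6 says that subjects know their group. No blinding of the investigator is described.

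**Data.** Screening (section 4.1) records "basic demographics, such as age, gender, and hand dominance". Sections 1.3 B, 1.9 and 1.10 list baseline information and then visual analogue soreness for each arm at 24, 48 and 72 hours. Weights, repetitions and sets are not listed.

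**Analysis.** Section 6.1 names a one-way repeated measures ANOVA at 0.05. It has no term for work or for hand dominance.

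**The concern.** The exercise produces the soreness that the trial measures. If one arm does more eccentric work than the other, the arms may differ in soreness before any oil is applied. The comparison of oiled with control arm takes that difference as part of the oil effect.

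Two features could make the gap systematic. Oil is always on the left, so any strength or endurance difference linked to dominance would tend to run the same way in most subjects. The treated arm is also known to both people whose judgement ends a bout.

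More work on the right would look like a benefit of oil; more work on the left would hide one. Repetitions and weights cannot be recovered once the session is over, so a gap that was not logged can be neither examined nor adjusted for.

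**Working it through.** **1. The plan's own figure.** Section 1.5 gives 20 subjects (10 per oil), 80% power and a one-tailed 0.05, with no effect size, SD or correlation, so 20 cannot be reproduced. Back-solving a paired t test (noncentral t, n=10) for 80% power gives a detectable effect of 0.85 SD one-sided or 1.00 SD two-sided, where SD is that of the within-subject left-right difference. The paired test is a simplified stand-in for the planned ANOVA.

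**2. False-positive rate under a work-driven shift.** Assume no oil effect and a systematic left-right shift of b SDs. The test statistic is noncentral t with n − 1 = 9 degrees of freedom and noncentrality b√10. The two-sided critical value is 2.262.

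The values of b are assumptions. One way to reach them is a mean soreness of 50 on a 0–100 scale, soreness proportional to work, and an SD of the difference of 15 to 20:
- 10% more work on one arm: 50 × 0.10 = 5 points; 5/20 = 0.25 and 5/15 = 0.33.
- 20% more work: 50 × 0.20 = 10 points; 10/20 = 0.50 and 10/15 = 0.67.

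| b (SD) | b√10 | Significant, two-sided | Significant in favour of oil, one-sided, if the shift favours oil |
|---|---|---|---|
| 0.25 | 0.79 | 11% | 18% |
| 0.33 | 1.05 | 16% | 25% |
| 0.50 | 1.58 | 29% | 43% |
| 0.67 | 2.11 | 47% | 62% |

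The nominal rate is 5%.

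**3. The opposite direction.** A true effect of 1.00 SD has 80% power two-sided. A work gap of 0.50 SD against the oil leaves 1.00 − 0.50 = 0.50 SD, and power falls to 29% (same row of the table).

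**4. Oil versus oil.** Oil type is randomised, so a left-right gap common to both groups cancels in expectation. What remains is the possibility that stopping decisions differ by oil, if the allocation is known during exercise.

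**5. What adjustment costs at n=10.** Let D be control minus oiled soreness and W the right-minus-left total work (sum of weight × repetitions). Fit D = a + cW with W uncentred, so that a is the oil effect at equal work. Let r be the correlation of D with W, and δ the mean of W in units of its SD. For normally distributed W, the variance of a relative to the unadjusted mean difference is

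(1 − r²) × [1 + (1 + nδ²)/(n − 3)].

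- δ = 0, r = 0.3: 0.91 × (1 + 1/7) = 1.04, a rise of 4%.
- δ = 0, r = 0.5: 0.75 × (1 + 1/7) = 0.86, a fall of about 14%.
- δ = 1, r = 0.5: 0.75 × (1 + 11/7) = 1.93.
- δ = 1, r = 0.3: 0.91 × (1 + 11/7) = 2.34.

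A simulation of 300,000 trials per case gave 1.04, 0.85, 1.92 and 2.33. The lost degree of freedom (critical value 2.262 to 2.306) comes on top. The large-sample reduction of r² (9% to 25% for these r) does not apply here.

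**The case against.** **The mechanism may be absent.** The text describes the subject's exercise and does not separate the arms. If both curl together with equal weights, repetitions match by construction and neither arm can be stopped early. This stands as a limit: the defect is that work is unspecified, unmatched and unlisted. It is not shown that work will differ. Even so, the same weight could be a different relative load for each arm.

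**Exhaustion may itself equalise the stimulus.** Taking both arms to exhaustion at the lightest weight is a common relative endpoint. A stronger arm might do more absolute work without proportionally more soreness, and weight × repetitions would then partly measure strength. This also stands. Proportionality is an assumption with no support in the documents, and it is one reason to keep adjustment as a sensitivity analysis.

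**Stronger readings that a reader might infer.**
- That the plan will produce a false oil benefit. The documents do not fix the direction of any gap, and a masked benefit is equally possible.
- That the investigator alone decides exhaustion. Section 1.3 names the participant's tolerance as well.
- That chance work gaps in 10 subjects would be a bias even with the side randomised. They would not: the test's error rate covers chance imbalance. The systematic part comes from the fixed side and from knowledge of the treated arm.
- That a work covariate buys power for one degree of freedom. Step 5 of the working shows otherwise.

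**Conclusion.** The concern holds in a limited form. Followed exactly, the plan would leave a left-right difference in eccentric work inseparable from an oil effect in the oil-versus-control contrast, with no record from which to check it afterwards. The oil-versus-oil contrast is much less exposed.

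The rates of 11% to 47% illustrate sensitivity; they do not predict this trial's error rate. They rest on assumed shifts of 0.25 to 0.67 SD and on a paired t test standing in for the planned ANOVA. The documents establish neither that a gap will occur nor its size or direction. The case for acting is that the information is cheap to collect and is lost if it is not collected. This is a recommended improvement and calls for no change to the exercise.

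**What to change.** Leave the exercise as described, and make three changes.

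1. **Sections 1.3 and 1.9:** record weight and repetitions for every set, separately for each arm. State whether the arms exercise together or in turn, and how work is matched, if it is.
2. **Section 1.3:** open the subject's oil allocation only after exercise ends. While the side is fixed, this hides the type of oil but not the treated arm, so it mainly protects the oil-versus-oil contrast. If the treated side is separately changed to be randomised, conceal the side until the same moment.
3. **Section 6.1:** report the between-arm work difference for each oil group. Prespecify a sensitivity analysis of the within-subject soreness difference with the uncentred work difference as covariate, reading the intercept as the oil effect at equal work. A centred covariate would leave the left-right contrast unadjusted. Keep the unadjusted contrast as the main analysis. If the log shows identical work in both arms, report that; the adjustment is then unnecessary.

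**Cost.** One tally sheet and one sealed envelope per subject. Section 1.3 already has the mixture prepared directly before application, so late opening should add little delay. The adjusted estimate may be less precise than the unadjusted one: its variance is about 4% higher at r = 0.3, about 14% lower at r = 0.5, and 1.9 to 2.3 times as large if the mean work gap equals one SD. It should be presented as a check on bias.

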6.0 Data Management Plan

6.1 Data Analysis

Treatment analysis will involve a 1-way repeated measures ANOVA. Differences will be considered significant when p values are below an alpha level of 0.05.

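### Oil always goes on the left arm and control on the right, so the oil-versus-control contrast is not randomised and cannot be separated from side

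*Combined protocol and SAP*

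**What the plan says.** Section 1.3 sets up a within-subject control: "Each subject will have one upper extremity serving as the control, and one upper extremity which receives the intervention". The Intervention part of that section then fixes the side: "the participants will have the respective oil applied topically to their left upper extremity by the investigator", and "Their right upper extremity will serve as the control and no essential oil will be applied".

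Randomisation is described once, also in section 1.3: "A blocked randomisation list will be generated using an online randomizer in order to allocate subjects to each treatment group randomly". The groups are the two oils, 10 subjects each. No section randomises, alternates or counterbalances the arm. Sections 1.6 and 1.10 mention intervention and control without naming a side, so they do not alter the left/right rule.

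The hypothesis in section 1.1 is that either oil "will reduce perceived muscle soreness in subjects compared to control". Soreness on a visual analogue scale (VAS) is the only endpoint. It is recorded for each arm at 24, 48 and 72 hours, and no pre-exercise score is listed.

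The screening survey in section 4.1 "identifies basic demographics, such as age, gender, and hand dominance", but dominance is used in neither allocation nor analysis. Section 6.1 says only: "Treatment analysis will involve a 1-way repeated measures ANOVA". It has no term for side or dominance.

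**The concern.** The only control in this trial is the subject's other arm. If every treated arm is a left arm, any systematic left-right difference in soreness after the exercise is counted as an oil effect. A less sore left arm would create an apparent benefit, and a more sore left arm would hide a real one.

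A difference between arms is plausible from the protocol's own procedure. Exercise runs to exhaustion through decreasing weights: "This will continue until subjects reach exhaustion with the lowest resistance weight". Both arms therefore finish at the same weight. Nothing in the plan, however, matches starting weight or repetitions between arms, or says whether the arms are exercised together, so total eccentric work may differ. Eligibility excludes recent resistance training and upper-extremity injury, which removes some asymmetry but not dominance.

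A common side effect would push both oil groups the same way, so similar results for the two oils would give no reassurance.

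**Working it through.** **The plan's own figure.** Section 1.5 gives 20 subjects for 80% power at one-tailed 0.05, with no effect size, SD or within-subject correlation, so it cannot be reproduced. Back-solving with the noncentral t, the standardised paired effect detectable at 80% power is:

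- n = 20: 0.58 one-tailed, 0.66 two-sided
- n = 10: 0.85 one-tailed, 1.00 two-sided

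**Structure (no assumptions needed).** Write each arm's expected score as intercept + oil effect × (oil on this arm) + side effect × (this arm is the left).

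- As planned, the oil and left indicators are identical in every row. The design matrix [1, oil, side] has rank 2 for three unknowns, so only oil effect plus side effect can be estimated.
- With the treated side balanced, the rank is 3 and the two effects separate.

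For dominance, let q be the right-handed proportion. The correlation between receiving oil and being the non-dominant arm is 2q − 1. Assuming q = 0.80, 0.90 and 0.95, oil falls on the non-dominant arm in 16, 18 and 19 of 20 subjects, and the correlation is 0.6, 0.8 and 0.9. This part of the confounding is partial.

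**Illustration 1: a pure left-right difference.** Assumptions: no oil effect; left arm less sore by b SDs of the within-subject difference; paired t-test in place of the ANOVA. The noncentrality is b√n; for b = 0.3 and n = 20 it is 0.3 × 4.472 = 1.34. Sections 1.5 and 6.1 leave the sidedness of the analysis open, so both are shown. Type I error:

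| b | n = 20, one-tailed | n = 20, two-sided | n = 10, one-tailed | n = 10, two-sided |
|---|---|---|---|---|
| 0 | 5.0% | 5.0% | 5.0% | 5.0% |
| 0.1 | 11.2% | 7.1% | 8.8% | 5.9% |
| 0.2 | 21.7% | 13.6% | 14.5% | 8.8% |
| 0.3 | 36.3% | 24.7% | 22.2% | 13.6% |
| 0.5 | 69.5% | 56.5% | 42.7% | 29.3% |

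**Illustration 2: a dominance difference.** Here the non-dominant arm is less sore by b, so the mean shift is (2q − 1)b, for example 0.8b at 18 right-handed to 2 left-handed. The results are simulated for n = 20, two-sided. The last column reverses the direction, with a true oil effect of 0.66 SD that would otherwise have 80% power.

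| b | Type I error, 18:2 | Type I error, 16:4 | Power, direction reversed, 18:2 |
|---|---|---|---|
| 0 | 5.0% | 5.0% | 80% |
| 0.1 | 6.3% | 5.6% | 69% |
| 0.2 | 10.2% | 7.6% | 56% |
| 0.3 | 16.7% | 10.9% | 42% |
| 0.5 | 36.4% | 20.1% | 17% |

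**Oil against oil.** Each group's oil-minus-control difference carries the same side effect, so it cancels between groups. With b = 0.5 and one left-hander per group, the simulated two-sided type I error is 4.1%, which is no inflation.

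**After the remedy.** The treated arm is balanced half and half, and the paired difference is regressed on treated arm with n − 2 degrees of freedom. Type I error is 4.9% to 5.1% at every b. Power goes from 80.0% to 79.7% (n = 20, two-sided) and from 80.1% to 79.1% (n = 10, one-tailed). If the term is left out, the balanced design is conservative: at n = 20, two-sided, type I error is 4.2% at b = 0.3 and about 2.9% at b = 0.5.

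**The case against.** The strongest reply is that nothing in the documents shows the arms differ. Taking each subject to exhaustion at the lowest weight may even out relative effort, and the exercise is adapted from a cited method that may settle arm order and loads. That is fair: unequal work is a possibility and not a finding, and the bias may be zero. But the plan itself contains nothing that would show it to be zero.

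A second reply is that dominance is recorded, so the paired difference could be regressed on handedness even with the left-arm rule. Under a pure dominance effect this does hold type I error at 5%. The price is high, because the effective sample is n[1 − (2q − 1)²]: 20 × 0.36 = 7.2 at 18:2 and 20 × 0.64 = 12.8 at 16:4. Power falls from 80% to about 39% and 61%. The adjustment fails if nobody is left-handed, and it cannot remove a pure side effect.

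Third, the objectives also include comparing the oils with each other, and that comparison remains randomised. This stands and limits the scope of the point.

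Fourth, randomising side does not make oil against control fully interpretable. Subjects know their treatment (section 1.6). In addition, section 1.3 puts no essential oil on the control arm while section 1.10 mentions control oils, and those passages must be reconciled. These are separate problems that the remedy does not cure, and they are no reason to keep an avoidable one.

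**Conclusion.** The concern holds and should be corrected before enrolment. The structural defect follows from the text alone: the only hypothesis is tested on a non-randomised contrast identical to left against right, and the resulting data cannot be repaired by analysis.

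The numerical consequences depend on assumptions that the documents do not supply: the size and direction of the arm difference, the handedness mix, and a paired t-test standing in for the planned ANOVA. Pooling both oils at n = 20 is also an assumption, since no pooled test is specified. Over 0 to 0.5 SD, with n = 20 and a two-sided test, type I error runs from 5% to 57% for a pure side effect and from 5% to 36% for a dominance effect at 18:2.

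**What to change.** - **Section 1.3, allocation.** Replace the fixed left/right wording. The oil goes on the arm (dominant or non-dominant) given by the randomisation list, and the other arm is the control. Add this as a column in the blocked list, giving four cells (oil × treated arm) of 5 subjects. Use block sizes in multiples of 4, for example 4, 8 and 8 in random order, which total 20.
- **Section 6.1, analysis.** State the adjustment precisely. Either regress each subject's control-minus-oil difference on treated arm coded +1/−1, or include arm dominance as a within-subject factor. A between-subject main effect of treated arm in per-arm data would not adjust the oil-control contrast.
- **Optional.** A pre-exercise VAS for each arm would show existing arm pain. It cannot show a difference in response to exercise, so it does not replace randomising the arm.

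**Cost.** One list column and wording changes in two sections. Dominance is already collected, section 1.10 names no side, and no extra subjects, visits or staff are needed. The investigator must check the list before each of the three applications. One degree of freedom is used, worth about one percentage point of power or less.
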